### **3.4 Ancillary MRI Imaging Analysis:**

The cardiac MRI images that are obtained to evaluate the secondary endpoint of this study provide an opportunity to analyze the utility of cardiac MRI vs. echocardiography. The baseline cardiac MRI images will be compared to the 3-month cardiac MRI images in both the cell treatment and control arms of this study to evaluate the secondary endpoint. The hypothesis that MRI is a more sensitive measure of sub-clinical cardiac dysfunction, patency of the surgical anastomoses, and pulmonary artery size compared to echocardiogram will be evaluated within this study by examining the available MRI and echocardiography imaging datasets obtained.

Specifically, paired cardiac MRI and echocardiograms collected at baseline and 3-months post Stage II surgery will be interpreted by the imaging core laboratory. Each site's images also will be available to their respective site investigators, without core lab interpretation for the purposes of adverse event reporting and clinical decisions. Site investigators will determine if the 3-month follow up cardiac MRI provides additional actionable insight beyond the echocardiogram images alone. The expectation is that additional detail related to cardiac function, performance of the conduit, and/or size of the pulmonary arteries that was missed completely or sub-optimally imaged with echocardiograms only. Actionable findings determined by the site investigator based on the availability of research MRI studies may lead to closer patient monitoring, medication changes, stenting procedures or even surgical corrections that could possibly improve the long-term outcome, and thus offer a potential benefit to subjects in both the treatment and control arms of this study. These actionable findings based on MRI studies at the sites will be documented in the study CRFs by surveying site investigators. The size and completeness of this dataset could define a new standard of care for post Stage II surgical evaluation that would not be possible without these MRI vs Echo images. Additional questions and data analysis may be performed by the imaging core to refine and validate site investigator finds as it relates to 3-month post-Stage II surgical MRI vs Echo studies, and de-identified MRI and echo images that are uploaded for analysis by the imaging core may be used for future research or shared with other researchers without additional informed consent.

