As part of a sub-group analysis, the images collected at 3-months post-Stage II surgery will provide a stand-alone analysis to test the hypothesis that MRI provides a more sensitive measure of sub-clinical cardiac dysfunction, pulmonary artery size, and patency of the surgical anastomoses. It is anticipated that nearly 10% of HLHS and HLHS variant patients may have actionable findings detected by MRI at 3 months post-Stage II surgery that would have been otherwise undetected with a standard of care echocardiogram. This sub-group analysis could provide the evidence to establish a new standard of care following Stage II surgery.

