 3 Tests/procedures will be performed daily during the hospitalization starting on Day 0. Continuous telemetry is not required on day of hospital discharge.  
 4 Laboratory tests, 12-lead ECG, and echo should be completed within 3 days of the discharge date. However, the laboratory tests, 12-lead ECG, and echo don't have to be repeated if the discharge date changes unexpectedly due to non-cardiac related issues.

- 5 To be conducted at 6 months post-Stage II surgery and every 6 months following the 12 month in-clinic visit for up to 4 years or until pre-operative Stage III work up or cardiac transplant.
- 6 Data to be collected from standard of care Stage III surgery pre-op work up in subject's medical records.
- 7 A subject will be considered enrolled on the study after completion of the procedural time-out.
- 8 Collection of medical history to occur up to enrollment. AE assessments to begin immediately following enrollment.
- 9 During Stage II Surgery hospital stay, changes in concomitant medications will not be recorded.
- 10 Includes weight, except for during post-op hospital stay
- 11 Includes temperature, heart rate, blood pressure and oxygen saturation. Temperature not required at 3 or 12-month in clinic visit.
- 12 Includes the following tests: High Sensitivity Troponin T, CRP, and NT-proBNP. On day 0, only the cardiac biomarker panel (High Sensitivity Troponin T) will be collected at 3 hr  $\pm$  30 min and 6 hr  $\pm$  30 min after enrollment.
- 13 Includes the following tests: RBC, WBC, Hemoglobin, Hematocrit, Platelets, Neutrophils, Lymphocytes, Monocytes, Eosinophils and Basophils
- 14 Includes the following tests: ALT, ALP, AST, Total Bilirubin, Albumin, Total Protein, BUN, and Creatinine.
- 15 Cardiac MRI will only be required at baseline. It is not required at 3 month visit or 12-month follow up. Baseline cardiac MRI should occur within 60 days prior to Stage II surgery.
- 16 When clinically available.
- 17 Questionnaires will be administered to participants at baseline and at 12, 24, 36 and 48 months post Stage II surgery for the duration of a subject's participation in the study.
- 18 Treatment arm only. Must occur within 5 days prior to cell delivery (see Sect. 6.1.2).
- 19 Required for both treatment and control arms (see Sect. 4.3).

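### Sections 2 and 3.4 plan a 3-month MRI-versus-echo analysis, but cardiac MRI is scheduled at baseline only, so the 3-month part has no scheduled data

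*Combined protocol and SAP*

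**What the plan says.** **What is planned.** Section 2 states that "the images collected at 3-months post-Stage II surgery will provide a stand-alone analysis" of whether MRI is the more sensitive measure of sub-clinical dysfunction, pulmonary artery size and patency of the surgical connections. It expects that "nearly 10% of HLHS and HLHS variant patients may have actionable findings detected by MRI at 3 months post-Stage II surgery" and suggests that the result could change standard care. Section 3.4 commits to three pieces of work:

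- A change-over-time comparison: "The baseline cardiac MRI images will be compared to the 3-month cardiac MRI images in both the cell treatment and control arms".
- A core-laboratory read: "paired cardiac MRI and echocardiograms collected at baseline and 3-months post Stage II surgery will be interpreted by the imaging core laboratory".
- A site judgement, recorded in the case report forms: "Site investigators will determine if the 3-month follow up cardiac MRI provides additional actionable insight beyond the echocardiogram images alone".

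Section 3.4 also presents the research MRI as a possible benefit to children in both arms and says the scans serve a secondary endpoint. It adds: "The size and completeness of this dataset could define a new standard of care for post Stage II surgical evaluation".

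**What is scheduled.** Footnote 15 in Section 6.5 reads: "Cardiac MRI will only be required at baseline. It is not required at 3 month visit or 12-month follow up". Section 6.1.1 lists cardiac MRI at baseline. Section 6.3.2 lists echo for the 3- and 12-month visits and no MRI. Appendix B covers echo at baseline, discharge, 3 and 12 months and before Stage III. Appendix C opens by covering MRI at baseline, although its image-acquisition paragraph still speaks of sequences at every time point.

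**The concern.** Two parts of the current text cannot both be carried out. A site that follows the schedule will not produce the 3-month scans that Sections 2 and 3.4 rely on. An analyst who follows Sections 2 and 3.4 will look for a dataset that the schedule does not create.

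Three things are at stake.

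1. **Selection.** A 3-month MRI could arise only outside the schedule. If such scans follow clinical need or site practice (an assumption; the documents do not say), they cannot give a cohort-wide yield of actionable findings or a sound comparison between arms.
2. **Claims made to ethics boards.** Section 11 sends this text to the IRBs. The potential benefit and the new-standard-of-care argument rest on a scan that the protocol does not require.
3. **An endpoint with no home.** Section 3.4 ties the MRI to a secondary endpoint, but Section 3.2 lists no MRI endpoint, and Section 7 says that Sections 3.2 and 3.3 describe the endpoints in full. The only listed endpoint that names MRI is item 6 of Section 3.3, at the Stage III work-up. The Clinical Study Summary version of that item omits MRI, and so does the collection list in Section 6.3.4.

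**Working it through.** **The plan's own figures.** The documents give no sample size, power or precision for the MRI analysis, and Section 7 contains no MRI method. The figures in Section 7.1 concern cardiac function at 3 months, which the primary endpoint measures by echo. They reproduce. With a two-sample t-test, 80% power and alpha 0.05 (taken as two-sided; the plan does not say), the smallest detectable standardized effect is 0.566 for 50 per arm. After 40% attrition, 50 × 0.6 = 30 per arm, and it is 0.736. The plan states 0.57 and 0.74. The MRI problem does not touch these figures.

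**Scheduled imaging, side by side.**

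| Time point | Echo | Cardiac MRI |
|---|---|---|
| Baseline | yes (6.1.1, App. B) | yes (6.1.1, fn 15, App. C) |
| Discharge | yes (6.2.3, App. B) | no |
| 3 months | yes (6.3.2, App. B) | no (6.3.2, fn 15) |
| 12 months | yes (6.3.2, App. B) | no (6.3.2, fn 15) |
| Stage III work-up | yes (6.3.4, App. B) | not in 6.3.4; named in 3.3 item 6 |

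The schedule grid is partly broken in the text available here, so this rests on footnote 15, the visit lists and the appendices.

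**Count of pairs.** Planned children: 2 × 30 = 60 to 2 × 50 = 100. A 3-month pair needs both modalities. Scheduled 3-month MRIs are 0, so scheduled 3-month pairs are 0 of 60 to 100. The baseline-to-3-month MRI comparison likewise has 0 scheduled pairs.

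**What the baseline pairs can answer.** They are taken before Stage II. They can compare the two methods for sub-clinical dysfunction and pulmonary artery size at that point. They cannot show patency of connections not yet made, or findings that arise after surgery.

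**Illustration of precision.** Take the expected yield as 10% and use exact (Clopper-Pearson) limits: lower = the 2.5% point of Beta(x, n − x + 1), upper = the 97.5% point of Beta(x + 1, n − x).

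| Scans n | Findings x | Exact 95% interval |
|---|---|---|
| 100 (all, upper plan) | 10 | 4.9% to 17.6% |
| 60 (all, lower plan) | 6 | 3.8% to 20.5% |
| 20 (assumed) | 2 | 1.2% to 31.7% |
| 10 (assumed) | 1 | 0.3% to 44.5% |

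The documents give no count of unscheduled scans, so the last two rows are illustrative only. None of the rows allows for selection bias. The plan sets no precision target for this yield.

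**The case against.** The best defence has four parts.

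- **Not required is not forbidden.** This stands. Section 3.4 speaks of "examining the available MRI and echocardiography imaging datasets obtained", Section 4.6 allows standard-of-care MRIs to be taken from records for subjects who stop active participation, and Appendix C still refers to all time points. Some 3-month MRIs may exist or arise. A reader might infer that the 3-month analysis is impossible, or that its hypothesis and survey must be deleted. The documents do not support that: deletion could discard a stated analysis of scans already held. However, scans of this kind cannot supply the completeness that Section 3.4 claims or a sound comparison in both arms. Section 4.6 is the only written route for collecting them, and it covers a selected group.
- **Baseline pairs remain.** This also stands, within the limits shown above.
- **It is only ancillary, and footnote 15 tells sites what to do.** Correct as to scope. It does not cure a benefit claim and an endpoint reference that the schedule does not support.
- **Stage III data may be missing by design.** Section 6.3.4 accepts this for its standard-of-care data. That is why item 6 can be aligned by keeping MRI where clinically available as well as by dropping it.

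A reader might also infer that the baseline-only schedule is the error. The documents do not show this. Appendix C gives MRI under general anesthesia, and Section 8.10 names a developmental concern with repeated anesthesia under 3 years of age. Section 1.4 reports that controls were deterred by a bundle of extra visits, blood tests and imaging; it does not isolate imaging, so it supports caution but no more.

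**Conclusion.** The text is wrong as written. Sections 2 and 3.4 commit to 3-month MRI work for which the protocol schedules 0 of 60 to 100 pairs, and Section 3.4 cites a secondary endpoint that Section 3.2 does not contain. Confidence in the contradiction is high, because it rests on plain prose in several sections and no other passage resolves it.

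The reach is limited to an ancillary analysis and the MRI component of the last-ranked long-term secondary endpoint. The echo and catheterization components of that endpoint stand. It would be wrong to infer any weakness in the efficacy conclusions from this point: the primary endpoints are measured by echo, and neither the power statement nor the stopping rules use MRI.

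The count of zero needs no assumption. That later scans would be a selected set is an assumption, and how many exist is unknown.

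**What to change.** Keep the baseline-only schedule and bring the text into line with it.

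1. In Sections 2 and 3.4, limit the planned MRI-versus-echo analysis to the baseline pairs. State that they precede Stage II and cannot assess its anastomoses or post-operative findings.
2. Relabel any 3-month MRI work, including the site survey, as opportunistic and descriptive, done where a 3-month MRI is available. Report by arm the number scanned and the indication, with no between-arm test and no cohort-wide yield claim.
3. Remove the statements about the size and completeness of the dataset and a new standard of care, the subject benefit that rests on 3-month research MRI, and the reference to a secondary endpoint.
4. Make Section 3.3 item 6 agree with the Clinical Study Summary and Section 6.3.4. Either drop MRI from item 6, or add MRI, when clinically available, to the other two. Both are sound; the second keeps a later comparator for the baseline scan.
5. Correct the reference to all time points in Appendix C.

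Restoring a 3-month MRI would also remove the conflict but is not proposed: it could add up to 100 general anesthetics, one per child.

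**Cost.** A text amendment submitted to the IRBs, with possible edits to the eCRF and, if it repeats the benefit statement, to the consent form (not visible here). No new scans, visits or anesthesia. The sponsor gives up the 3-month MRI claim.

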## 4 SUBJECT ELIGIBILITY ASSESSMENTS, ENROLLMENT, AND WITHDRAWING SUBJECTS

### 4.1 Eligibility for This Study:

Both sexes with HLHS or HLHS variants with right ventricular dependent single ventricular CHD requiring planned Stage II surgical repair that meet the following inclusion and exclusion criteria are eligible to participate in this study. Inclusion and exclusion requirements may be specific to the treatment arm only and will be specified as such in parentheses.

#### 4.1.1 Inclusion Criteria

1. Diagnosis of HLHS or HLHS variant with single right ventricular dependent CHD having undergone Stage I surgical repair and undergoing Stage II surgical repair.
2. Less than 13 months of age at time of Stage II surgical repair.
3. Previous participation in the UCB collection protocol with autologous UCB-MNC product that is acceptable for use (treatment arm only).

#### 4.1.2 Exclusion Criteria

1. History of DMSO reaction (treatment arm only).
2. Parent(s) and/or legal guardian(s) unwilling to have their child participate or unwilling to follow the study procedures.
3. Severe chronic diseases at the discretion of the treating physician.
4. Extensive extra-cardiac syndromic features.
5. Known history of cancer.
6. Any of the following complications of his/her congenital heart disease:
  - a. Any condition requiring urgent, or unplanned interventional procedure within 15 days prior to Stage II surgical repair, unless complete and full cardiac recovery is documented by site investigator
  - b. Severe pulmonary hypertension (reported in the medical record as >70% systemic pressure)
  - c. Other clinical concerns as documented by a site investigator that would predict (more likely to happen than not to happen) a risk of severe complications or very poor outcome, not directly related to the stem cell product or its injection procedure, during or after Stage II surgical repair.

### 4.2 Consent/Screening

Potential subjects for the treatment arm (Arm A) of this study will be pre-screened from the Umbilical Cord Blood collection study. Parent(s) and/or legal guardian(s) of a child with HLHS or HLHS variant with single right ventricular dependent CHD requiring Stage II surgical repair, whose UCB-MNC has been documented to be acceptable for release to the investigational site, and whose child appears to meet the other study eligibility criteria (Section 4.1) during pre-screening may be consented to allow their child to participate in the treatment arm of this study.

Potential subjects for the control arm (Arm B) will be pre-screened during cardiology visits when Stage II surgery is being scheduled at the investigational site. Otherwise, potential subjects for the control arm will be pre-screened from the Umbilical Cord Blood collection study when their product is documented to not be acceptable for release to the investigational site. Parent(s) and/or legal guardian(s) of a child with HLHS or HLHS variant with single right ventricular dependent single ventricular CHD requiring Stage II palliative reconstructive surgery and whose child appears to meet all other study eligibility criteria (Section 4.1) during pre-screening may be consented to allow their child to participate in the control arm of this study.

Consent will occur after the parent(s) and/or legal guardian(s) have discussed the study with the study staff, a site investigator has pre-screened subject eligibility, and the parent(s) and/or legal guardian(s) have been provided adequate time and information to decide if they would like their child to participate. If both parent(s) and/or legal guardian(s) do not sign informed consent, the reason for only one parent or legal guardian signing should be documented at the time of informed consent. Consent must occur before any study procedures are completed, however standard of care procedures done within 30 days prior to Stage II surgery may be used rather than repeating procedures to collect study data. The original signed informed consent will be filed in the subject file and a copy will be given to the parent(s) and/or legal guardian(s). The informed consent process will be documented and provided in the subject file.

All subjects will enter screening phase at the time of informed consent.

#### **4.3 Enrollment/Procedural Timeout**

Enrollment in either arm of this study will occur at the Procedural Timeout. The Procedural Timeout will be conducted in the operating room, by a trained site investigator, following the completion of the Stage II repair. During the Procedural Timeout, a site investigator will confirm all inclusion and exclusion criteria have been met per Section 4.1 of this protocol and document his/her decision to enroll the subject. If the site investigator determines that the subject, in either arm, fails to meet all inclusion and exclusion criteria, the subject will be declared a screen failure (see Section 4.5) and exited from the study. A subject should not be enrolled in either arm of the study if the subject has surgical complications during the Stage II repair that result in, or could be reasonably expected to result in, significantly decreased cardiac function.

For the treatment group, if a subject is determined to be eligible to enroll, the Procedural Timeout will also include confirmation that the subject's identity matches the patient identifiers on the investigational product label, confirmation of the number of injection sites and product volume to be delivered, and confirmation that there aren't any anticipated complications or concerns.

#### **4.4 Time of Treatment (Treatment Arm Only)**

For subjects enrolled in the treatment arm, thawing of the product and the cell delivery procedure will occur immediately following the Procedural Timeout. A subject is considered treated at the time that cell delivery injections begin. If only a partial cell delivery occurs, the subject will still be considered treated and will be followed as planned according to the procedures described in

Section 6 of this protocol. The cell delivery procedure will be entered in the eCRF and the reason(s) for failing to deliver a full dose, if applicable, will also be documented in the eCRF.

#### **4.5 Screen Failures**

Subjects will be considered screen failures if they fail to meet one or more of the study eligibility criteria. Screen failures will be tracked and monitored to facilitate in assessing the feasibility of the overall study. Screen failures will be documented in the eCRF. Screen failures do not count toward the study enrollment cap of 50 subjects in each arm.

#### **4.6 Discontinuation and Withdrawal Subjects**

A subject will be considered a lost to follow-up subject after three documented attempts (the third attempt will be a certified letter) have resulted in failure to contact the parent(s) and/or legal guardian(s).

For the treatment arm, subjects will be discontinued from the study if there is a compromise to the cell product (see Section 5.4.2) following subject enrollment.

Parent(s) and/or legal guardian(s) may decide to withdraw their child from the study at any time during participation in the study. If the parent(s) and/or legal guardian(s) request that their child be withdrawn from the study, the Sponsor will utilize data collected up to that time point but will discontinue future study follow-up assessments. Survival status data will be collected through search of public records by the enrolling site. If a subject has discontinued from active participation but not from the study, standard of care echocardiograms, MRIs, cardiac catheterizations, ECGs, laboratory tests, weight/vitals, and new or worsening conditions that are normally collected for this study will be collected from the subject's medical records, if the parent(s) and/or legal guardian(s) have previously consented to this additional collection of standards of care data. This data is important to ensure there are no safety issues and to monitor for evidence of efficacy in subjects that have decided to withdraw from active participation in the study. Withdrawn subjects and subjects that discontinue from active participation but not from the study will be documented in the applicable eCRF. Documentation must be provided in the subject study chart for any study withdrawal or discontinuation.

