The investigational product will NOT be used if there is any significant exposure to an unsterile field or potential compromise to the integrity of the cells, the container leaking, a failure to maintain the cells as a frozen stock prior to intentional thawing or greater than 30 minutes from the time product is started to be thawed to the beginning of injections. If a redundant back-up vial is not available in the surgical suite to replace the compromised vial of cells, then the cell delivery procedure will be cancelled.

The Sponsor and the site investigator (cardiac surgeon) performing the cell delivery procedure will be notified immediately of any discrepancies, damage or unusable product that is received prior to commencing the delivery of cells.

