### 7.2 Subject Population(s) for Analysis

Only consented and eligible subjects will be used in analysis. Safety analysis will be based upon all subjects who undergo surgery and receive any volume of cell delivery (partial or full) and have follow-up data in the cell-therapy group and all subjects who have follow-up data in the control group. Efficacy analysis will be based upon all subjects who receive full cell delivery and have follow-up data in the cell-therapy group and all subjects who have follow-up data in the control group.

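### Enrolled Arm A children whose product is compromised leave the study and both analysis sets; no matching rule applies to controls, and no as-enrolled check is possible

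*Combined protocol and SAP*

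**What the plan says.** - **Enrolment (4.3).** "Enrollment in either arm of this study will occur at the Procedural Timeout", in the operating room after the Stage II repair. Children with surgical complications that threaten cardiac function are kept out of both arms at that point.
- **Thaw (4.4).** In Arm A, "thawing of the product and the cell delivery procedure will occur immediately following the Procedural Timeout". Any compromise arising at or after thaw therefore affects a child who is already enrolled.
- **Product not to be used (5.4.2).** The listed causes are unsterile exposure or possible loss of cell integrity, a leaking container, failure to stay frozen, and "greater than 30 minutes from the time product is started to be thawed to the beginning of injections". Delivery is cancelled under a condition: "If a redundant back-up vial is not available in the surgical suite to replace the compromised vial of cells".
- **Discontinuation (4.6).** The rule, for Arm A only, is that "subjects will be discontinued from the study if there is a compromise to the cell product". It applies once the child is enrolled and points to 5.4.2. The back-up vial condition is not repeated.
- **Data after leaving (4.6).** Chart data are collected for children who stop active participation but remain in the study. The public-records survival search appears in the text on parental withdrawal. Neither is stated to cover a child discontinued for product compromise.
- **Partial delivery (4.4).** "If only a partial cell delivery occurs, the subject will still be considered treated and will be followed as planned".
- **Analysis sets (7.2).** "Efficacy analysis will be based upon all subjects who receive full cell delivery and have follow-up data in the cell-therapy group". The Arm A safety set needs at least some delivered volume. Controls need only follow-up data for either set.
- **Attrition (7.1).** The second power scenario assumes 40% attrition or incomplete data, the same in both arms.

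**The concern.** The Timeout gives both arms a common starting point, and its screen for surgical complications works before enrolment in both. Section 4.6 adds a second filter after that point, in Arm A only. A control whose condition worsens shortly after the Timeout stays in follow-up and in the analysis. An Arm A child whose injections are held up past 30 minutes for the same reason, with no replacement vial, leaves the study. If the same event happens just after the first injection, the child counts as treated and is followed.

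Two things are at stake. If any of these removals depend on the child's condition, the Arm A mean is taken over a selected group. And because follow-up ends, nobody can later test whether that mattered: an as-enrolled analysis would have no 3-month echocardiogram for these children.

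**Working it through.** **1. The plan's own figures.** Section 7.1 gives 80% power at alpha 0.05 for effects of 0.57 (50 per arm) and 0.74 (30 per arm, since 50 × 0.60 = 30). A two-sided two-sample t-test gives detectable effects of 0.566 and 0.736, so both figures reproduce. One-sided alpha 0.05 gives 0.50 and 0.65, which do not match. The plan is therefore taken as two-sided.

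**2. Which section does what.**

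| Child, after enrolment | Followed? | Safety set? | Efficacy set? |
|---|---|---|---|
| Arm A, full delivery | yes | yes | yes |
| Arm A, partial delivery | yes (4.4, 5.4.2) | yes | no (7.2) |
| Arm A, discontinued for compromise, no cells given | none stated (4.6) | no (7.2) | no (7.2) |
| Arm B, any intra-operative event after the Timeout | yes | yes | yes |

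Membership of either set also requires follow-up data. Exclusion from the primary analysis comes from 7.2. Loss of the data needed for any other analysis comes from 4.6. Changing 4.6 alone would leave the primary estimate as it is.

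**3. Precision.** Let k be the number of Arm A children removed and not replaced, with all 50 controls retained (t-test, effect 0.57).

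| k | Arm A n | Power | Detectable effect |
|---|---|---|---|
| 0 | 50 | 80.6% | 0.566 |
| 1 | 49 | 80.2% | 0.569 |
| 2 | 48 | 79.7% | 0.572 |
| 3 | 47 | 79.3% | 0.575 |

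Loss of power is negligible.

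**4. Selection.** Suppose k of 50 are removed and would have scored D SD below the remaining children. The mean of all 50 is then (k/50) × D below the mean of those who remain, so removal raises the Arm A mean by k × D / 50. **Assumption:** k = 0 to 3 and D = 0 to 2; neither is in the documents. D is an average over all removed children, including those with pure product faults, for whom it may be near zero.

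The rejection rate when there is no true effect uses a normal approximation with unit SD and SE = √(1/(50 − k) + 1/50).

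| k | D | Shift (SD) | SE | Two-sided rejection rate |
|---|---|---|---|---|
| 0 | any | 0 | 0.200 | 5.0% |
| 1–3 | 0 | 0 | 0.201–0.203 | 5.0% |
| 1 | 1 | 1 × 1/50 = 0.02 | 0.201 | 5.1% |
| 2 | 1 | 2 × 1/50 = 0.04 | 0.202 | 5.4% |
| 3 | 1 | 3 × 1/50 = 0.06 | 0.203 | 6.0% |
| 3 | 2 | 3 × 2/50 = 0.12 | 0.203 | 9.1% |

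The upper corner, 0.12, is 0.12/0.57 = 21% of the planned detectable effect. It requires three removals, all from a strongly prognostic cause.

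**5. The two triggers side by side.** Section 4.6 discontinues on a compromise to the product. Section 5.4.2 lets a back-up vial replace a compromised one and cancels delivery only if none is in the surgical suite. Read literally, a child dosed from a back-up vial would be treated under 5.4.2 and discontinued under 4.6. The passages must be reconciled.

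**The case against.** The strongest reply is that this will rarely happen and has little to do with prognosis.

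- A back-up vial can avert cancellation, although Appendix A says the number of aliquots varies by child.
- Most of the listed causes concern the product, not the child.
- Serious surgical complications have already been screened out in both arms, and in Arm A the Timeout also confirms that no complications or concerns are anticipated.
- Appendix A puts a hand thaw at about 3 to 5 minutes, so an overrun of 30 minutes has many possible logistical causes.
- Instability after the first injection leads to follow-up, not removal.
- Assignment is not randomised, so no randomised comparison is broken.

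All of this stands as an argument about size. The one prognostic route left is instability between thaw and first injection that outlasts 30 minutes with no usable back-up. That route is narrow but open, and it exists in one arm only.

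A reader might also infer that safety data are thrown away. The documents do not say so. Adverse events are recorded from enrolment, unresolved events are followed (8.7), discontinuations must be documented, and the DSMB receives adverse event and withdrawal tables (8.13). What is missing is later outcome follow-up and a place in the safety set.

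**Conclusion.** The point holds as a minor one. Sections 4.6 and 7.2 together make a post-enrolment exclusion that applies only to Arm A, contrary to the equal attrition assumed in 7.1, and 4.6 prevents any later check of its effect.

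It is tempting to go further and say that the rule biases the comparison toward the product. The documents do not support that. They do not link delay to the child's condition, and they give no count and no prognosis. The shift of 0 to 0.12 SD rests wholly on the assumed 0 to 3 children and 0 to 2 SD, and zero is a credible value. Nor does every compromise, or every delay beyond 30 minutes, necessarily mean cancelled delivery, because of the back-up vial clause. The disagreement between 4.6 and 5.4.2 is a matter of text and depends on no assumption.

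**What to change.** 1. **Section 4.6.** State that enrolled Arm A children whose cell delivery is cancelled remain in the study for outcome collection, on the existing visit schedule or at least through the chart-data route already in 4.6, which needs prior parental consent. The visit schedule secures the 3-month echocardiogram at the planned time. The chart route is lighter for a child who received no cells, but yields only what standard care provides.
2. **Sections 4.6 and 5.4.2.** Reconcile the trigger, so that it is clear whether a compromised vial that is replaced leads to discontinuation.
3. **Section 7.2.** Report these children as *enrolled, not treated*, with their number, reasons and adverse events. Add a sensitivity analysis of the primary endpoint as enrolled, with them and the partial deliveries counted in Arm A. Also state whether they count toward the cap of 50; section 4.5 exempts only screen failures.

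The primary analysis and the rule on when product may be used stay unchanged. The cost is follow-up of probably a few undosed children, with the burden of study visits if that route is chosen, and slight dilution of Arm A in the sensitivity analysis only.
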